Feasibility Assessment of the Wake Forest Real-time Tracking System for Monitoring
Patient Movement during Postoperative Recovery: Part 2
IRB 00039439

Documentation Date: 6/30/2019

IRB: 00039439

NCT03988751

Feasibility Assessment of the Wake Forest Real-time Tracking System for Monitoring
Patient Movement during Postoperative Recovery: Part 2
IRB 00039439

Principal Investigator: [name]
Department of General Surgery
Section of Surgical Oncology
Wake Forest University School of Medicine
[name]
[name]
[contact]
[contact]

Staff: [name]

Biostatistician: [name]
[contact]

Participating Institution(s): Wake Forest University

Version Date: 6/30/2019

Confidential

Summary

The proposed study will investigate the feasibility of using the Wake Forest Real-time Location System (RTLS) in monitoring patient movement during their in-hospital postoperative recovery. The study will involve patients who have undergone surgery requiring inpatient admission to the 9CC surgical ward. Actual patient movement will be monitored during their postoperative recovery and compared with data recorded by the Wake Forest location system.

1.0 Introduction and Background

Early mobilization after surgery can decrease postoperative complications and length of stay. Recognizing these improved outcomes, current enhanced-recovery after surgery (ERAS) programs emphasize rapid mobilization during the postoperative period even on the day of surgery.(1–3) Unfortunately, patients face numerous real and perceived barriers to early mobilization including postoperative pain; multiple intravenous catheters; drains; lines, and staff resource limitations. Monitoring compliance with early mobilization programs rely on patient self-report, progress notes, and nursing documentation, all of which are unreliable. Our team has used accelerometers (Fitbit Zip and Kenz Lifecorder) to monitor postoperative movement after major gastrointestinal oncology surgery (CCCWFU 02114). Preliminary data from this study, demonstrates little to no movement by patients during their hospitalization. However, this may be an artifact of current accelerometer devices rather than lack of movement by patients.

In an era of the Internet of Things (IoT) and emerging technologies, we recognized a unique opportunity to use the existing real-time location system (RTLS) at Wake Forest Baptist Health to monitor patient movement during postoperative recovery.(4) The Wake Forest Office of Enterprise Visibility developed a program for the implementation of processes, supporting technologies, driving Service Excellence, Patient Safety and Satisfaction, Operational Excellence and Efficiency, and the Transformation of Healthcare Delivery (SPOT). The SPOT program installed the current real-time location system throughout Wake Forest Baptist Health initially to track high valued hospital assets. RTLS is a complex system of various tags and badges, platforms (Wi-Fi, Infrared, Ultrasound, and others), hardware infrastructure (readers & excitors) and other components (servers, middleware & end-user software).(5) The Wake Forest RTLS solution consists of specialized fixed location sensors receiving wireless signals from small ID badges or tags attached to equipment or persons. Tags transmit a unique identifier in real-time that enable tracking. The granularity of the RTLS program varies throughout the health system with room-level tracking capabilities in the wards of the Wake Forest Comprehensive Cancer Center.

Feasibility Assessment of the Wake Forest Real-time Tracking System for Monitoring Patient Movement during Postoperative Recovery: Part 2
IRB 00039439

The RTLS program at Wake Forest Baptist Health was introduced for asset tracking and not developed for monitoring patient movement. Therefore, the reliability of this system is unknown but has great potential for numerous quality improvement initiatives particularly focused on decreased postoperative complications and successful implementation of early recovery after surgery programs.

2.0 Objectives

The main objective of the proposed study is to investigate the feasibility of using the Wake Forest RTLS to monitor movement of hospitalized patients after surgery. Preliminary data from this prospective cohort study will help determine reliability, accuracy, sensitive and specificity of the RTLS system during the implementation of an in-patient postoperative exercise program.

3.0 Aims

3.1 Primary Aim

- 3.1.1 To demonstrate the feasibility of using the Wake Forest RTLS to track patient movement during the postoperative period.

3.2 Secondary Aims

- 3.2.1 To evaluate the accuracy of the RTLS to track distance and time traveled during a patient walk on the hospital ward.
- 3.2.2 To characterize daily movement (speed, steps, frequency, distance) of in-hospital post-surgery patients.
- 3.2.3 To evaluate patient perspective on in-hospital exercise programs.
- 3.2.4 To characterize provider perspective on in-hospital exercise programs, monitoring patient movement, and reporting patient movement.
- 3.2.5 To evaluate the accuracy of the RTLS to track patient movement at variable patterns of movement.
- 3.2.6 To evaluate patient tolerance of continuous verses interval exercise program.
- 3.2.7 To characterize subject readiness for discharge.

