5.6 Walking Assessment and Physical Activity Survey (Observational Cohort)

All participants will receive a visit by a study team member each day for maximum of 3 days. If discharge is less than 24 hours after enrollment, the participant will be excluded from study. Study participants will be invited by a study team member to join them on a walk. Time, distance, and duration will be determined by the patient. If nursing staff or treating provider determines that walking is not safe or inappropriate, walk will not be performed and rationale documented. If patient declines to walk, rationale will be documented. For all patients who decline, a second visit by a study team member will occur later in the day. Participants will be encouraged to walk by study team members emphasizing the importance of walking after surgery. Each participant will complete a pre- and post-walk assessment including measurement of pain and fatigue. Pre- and post-walk vital signs will be recorded. Participants will also be asked to report number of walks completed in the last 24 hours along with distance traveled. At completion of walk, the study team will record exact time of walk, distance, and duration. At conclusion of walk assessment, the patient will complete a physical activity in hospital survey. Survey data will be collected in the subject's private room.

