5.7.4 Ambulatory Session

Each subject perform one ambulatory session during the study. This will include walking 40 meters. Gait speed will be calculated using the speed

Feasibility Assessment of the Wake Forest Real-time Tracking System for Monitoring Patient Movement during Postoperative Recovery: Part 2
IRB 00039439

in which the subject walked 40 meters. Alternative exercise (hand bike) will be provided if subject declines ambulation or unable to ambulate out of their room. Demonstration of the hand bike will be provided by the study team member and subjects will be allowed to practice with the bike prior to exercise session. For subjects unable to perform the ambulatory session, a study team member will return on a subsequent hospital day to complete this portion of the study. If patient unable to perform the ambulatory session during their hospitalization or during the study period, the reason will be documented.

1. Walking Continuous Training (Group 1): The total distance will be 40 meters. Study team members will walk, support, and coach the subject to walk as slow as he/she wants.
2. Walking Interval Training (Group 2): The subject will walk a total distance of 40 meters. This distance will be divided into four intervals of 10 meters to equal the same measured distance as the continuous group. The subject will receive two minutes of rest between each interval and will be supported and coached to walk as fast as they can.
3. Hand Bike Continuous Training (Group 1, alternative option until able to participate in ambulatory session): The subject will be asked to bike for 5 minutes continuously with coaching “go as slow as you want.”
4. Hand Bike Interval Training (Group 2, alternative option until able to participate in ambulatory session): The subject will be asked to bike in 10 second intervals (“as fast as they want to go”) and rest for 50 seconds for five rounds (i.e. every minute on the minute (EMOM)).

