6.0 Outcome Measures

- 6.1 Primary Outcome: Determine if the SPOT system can detect movement in and out of a patient's room.
- 6.2 Secondary Outcomes:
 - 6.2.1 Characterize patterns of patient movement after surgery.
 - 6.2.2 Characterize number of times of patient exits a room per day after surgery.
 - 6.2.3 Characterize distances traveled per time out of room per day after surgery.
 - 6.2.4 Characterize patient opinion regarding exercise after surgery.
 - 6.2.5 Characterize provider opinion regarding in-hospital exercise programs, monitoring patient movement, and reporting patient movement.
 - 6.2.6 Determine if the SPOT system can detect movement when a patient varies their ambulatory behavior.
 - 6.2.7 Characterize patient's ability to tolerate various ambulatory intensities after surgery.
 - 6.2.8 Describe patient readiness for discharge.

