The study team will also capture information from this pilot study that will be used to improve the efficiency of larger studies. We will evaluate the capabilities of the SPOT system to monitor patient movement. Feasible study will be defined as more than 80% of badges assigned to the observational study participants will detect movement in and out a room. All data will be descriptive in nature and will focus on patterns of movement and presence or absence of data. Summary statistics such as means and standard deviations will be calculated for continuous measures and counts and percentages will be calculated for discrete measures. Agreement statistics, including kappa statistics, sensitivity, and specificity, will be calculated. Changes of pre- and post- vital signs will be calculated and graphical display will be performed to show the changes over time. The correlation between walking distance as well as pain and fatigue will be calculated each day. Mixed effects models will be used to study the association over time. Since the sample size is small, we are aware that the models may not be stable. Thus, descriptive analysis will be our primary analysis.

The additional HITT study cohort will enable validation of SPOT system to capture out of room events under various ambulatory patterns. This will build on the current cohort that validated simple in and out of room events. Feasible study will be defined as more than 80% of badges assigned to participants detect movement in and out a room during continuous and interval movement patterns.

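### Aim 3.2.1 asks how accurately the RTLS measures distance and time, but the named agreement statistics suit yes/no detection and no planned analysis compares RTLS values with the recorded walk

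*Combined protocol and SAP*

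**What the plan says.** - **The aim.** Section 3.2 lists as Aim 3.2.1: "To evaluate the accuracy of the RTLS to track distance and time traveled during a patient walk on the hospital ward".
- **The agreement analysis.** Section 7.2 states: "Agreement statistics, including kappa statistics, sensitivity, and specificity, will be calculated". It gives no other agreement method and no acceptable error.
- **Continuous data.** Section 7.2 states: "Summary statistics such as means and standard deviations will be calculated for continuous measures". The only use it names for walking distance is its association with pain and fatigue, by daily correlation and by mixed models.
- **The outcomes.** Section 6.0 has no outcome for accuracy of distance or time. The nearest, 6.2.3, is descriptive: "Characterize distances traveled per time out of room per day after surgery".
- **The reference data.** For the observational cohort, Section 5.6 states: "At completion of walk, the study team will record exact time of walk, distance, and duration". For the HIIT cohort, Section 5.7.4 fixes the distance: "This will include walking 40 meters".
- **The promised comparison.** The Summary states: "Actual patient movement will be monitored during their postoperative recovery and compared with data recorded by the Wake Forest location system". No method is attached to it.
- **The resolution of the system.** Section 1.0 describes "room-level tracking capabilities in the wards of the Wake Forest Comprehensive Cancer Center". No section says how such data become a distance.

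**The concern.** Kappa, sensitivity and specificity need both the RTLS reading and the reference to be sorted into categories, such as exit or no exit. They can show whether the system noticed that a patient left the room. They cannot show by how many metres or seconds its account of the walk was wrong. Separate means and SDs for each source do not show this either: over-reading on some walks and under-reading on others can cancel in the means and leave no trace of the error on any one walk.

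Section 2.0 lists accuracy alongside sensitivity and specificity, so the protocol itself treats them as different properties. At stake is whether the study can say anything quantitative about distance and time, which a later exercise study would need if it used RTLS distance as a measure of mobility.

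**Working it through.** **1. The plan's own figure.** The only power statement (Section 7.1) concerns sensitivity or specificity: 20 subjects, two-sided 0.05, null value 0, alternative 0.9, prevalence 0.3, power above 90%. With a null of 0, a single detection rejects, so power = 1 − (1 − 0.9)^m for m positives.
- Prevalence 0.3: m = 20 × 0.3 = 6, power = 1 − 0.1^6 = 0.999999.
- Prevalence 0.1 (or 0.9 for specificity): m = 2, power = 1 − 0.1^2 = 0.99.

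With a fixed number of positives the claim reproduces. It concerns yes/no detection only. No figure is given for distance or time. (The choice of 0 as the null is a separate matter.)

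**2. What the named statistics would miss.** This is an illustration with assumed data. Let 40 walks be spread evenly over 40 to 200 m, with the RTLS reading half the true distance plus noise of SD 5 m.
- Every walk registers, so detection sensitivity = 1.00.
- Expected bias = −0.5 × (40 + 200)/2 = −60 m.
- SD of differences = sqrt[(0.5 × 160/√12)² + 5²] = sqrt(533.3 + 25) = 23.6 m.
- Expected 95% limits of agreement = −60 ± 1.96 × 23.6, or about −106 to −14 m.

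One simulated set of 40 such walks gave sensitivity 1.00, bias −60.8 m and limits −108 to −13 m. The named statistics would report perfect performance.

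**3. What the collected data could support.** Take one usable walk per patient and work in units of the SD of the paired differences, which the documents do not give.
- Half-width of the 95% CI for mean bias: t/√n.
- Half-width for each limit of agreement: t × sqrt[1/n + 1.96²/(2(n − 1))].
- For n = 40, t = 2.023: bias 2.023/√40 = 0.32 SD; limit 2.023 × sqrt(0.0250 + 0.0493) = 0.55 SD. The shortcut 1.96 × sqrt(3/40) gives 0.54 SD.

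| Patients with a usable walk | Bias (± SD) | Each limit (± SD) |
|---|---|---|
| 40 (observational, all) | 0.32 | 0.55 |
| 22 (HIIT, all) | 0.44 | 0.77 |
| 20 (assumed: half of the observational cohort) | 0.47 | 0.81 |

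If the SD of distance differences were 5, 10 or 20 m (assumed range), n = 40 would give half-widths of 0.32 × SD = 1.6, 3.2 or 6.4 m for bias and 0.55 × SD = 2.8, 5.5 or 11.0 m for each limit.

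**4. Limits on these numbers.** Section 5.6 lets walks be declined or withheld, and Section 5.7.4 offers a hand bike to those who cannot walk, so 40 and 22 are upper bounds on patients. Up to three walks per patient (Section 5.6) would add some precision. How much depends on the within-patient correlation, which is not given.

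**The case against.** The strongest reply has four parts.

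- **The list is open.** Section 7.2 introduces the three statistics with the word *including*, it plans summaries of continuous measures, and the Summary promises a comparison with actual movement. A reader might infer from the mismatch that Aim 3.2.1 cannot be answered. The documents do not support that, because the paired reference values are collected and a descriptive answer is possible. This part stands. But an open list is not a method: with no comparison and no acceptable error stated, both would be chosen after the data are seen.
- **No false claim is planned.** A reader might also infer that exit-detection results will be presented as proof of distance accuracy. Nothing in Sections 6.0 or 7.2 says so. The feasibility criteria are confined to badges detecting movement in and out of a room. This part stands too.
- **This is one secondary aim in a descriptive pilot.** That is true, and it limits the weight of the point. A descriptive study still needs to describe the quantity named in its aim.
- **The RTLS may yield no distance in metres.** With room-level tracking this is a fair caution, and it shapes the remedy: the derivation has to be defined before any comparison of distance. Time can be compared either way, but staff record walk duration, not time out of the room, and the two need not coincide.

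Bland-Altman is also not the only suitable choice. Mean error, percentage error or an intraclass correlation could be argued for. Bias with limits of agreement is preferred here because it gives the error in metres and seconds.

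**Conclusion.** The point holds as a gap in the specified analysis. Every agreement statistic named is categorical, the sample-size reasoning concerns detection only, and no planned analysis sets RTLS distance or time against the staff-recorded walk. Followed to the letter, the plan yields no estimate of error for Aim 3.2.1, however well the system detects exits.

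The gap can be closed with data the protocol already collects. Whether a half-width of 0.32 SD for bias and 0.55 SD for each limit is tight enough cannot be judged from the documents, because they give neither the SD of the differences nor an acceptable error. Both figures assume 40 patients with one usable walk each. The point should be corrected, but it does not touch the primary outcome or the feasibility criteria.

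**What to change.** In Section 7.2:

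1. Reserve kappa, sensitivity and specificity for room-exit detection.
2. For Aim 3.2.1, add a paired-difference (Bland-Altman) analysis of RTLS minus staff-recorded walk duration (s). Where an RTLS distance can be derived, do the same for RTLS minus staff-recorded distance (m), or minus 40 m in the HIIT cohort.
3. Report mean bias and 95% limits of agreement with confidence intervals. Allow for up to three walks per patient in the observational cohort, for example with a patient random effect. Use a percent or log scale if error grows with distance. This has to be judged in the observational cohort, because the HIIT distance is constant.
4. State how RTLS distance is derived from room-level data. If it cannot be derived, limit the aim to time.
5. For time, define how the RTLS out-of-room interval is aligned with the recorded start and duration of the walk. For interval walkers, say whether the three two-minute rests (3 × 2 = 6 minutes) count.
6. State what error would be acceptable, or say that none is set and the result is an estimate only.

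The cost is modest extra analysis work, mostly to define the derived distance and match the time windows. No further patients or procedures are needed. The observational cohort is closed to enrolment, so these choices should be fixed before the paired differences are computed.

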4.0 Study Population

Feasibility Assessment of the Wake Forest Real-time Tracking System for Monitoring
Patient Movement during Postoperative Recovery: Part 2
IRB 00039439

The proposed study is a prospective, **observational** cohort study investigating the feasibility of using the Wake RTLS to monitor postoperative patient movement. All patients will be recruited from the surgical ward of the Wake Forest Baptist Health (9cc). All patients will have undergone elective surgical intervention with anticipated minimum of 24 hours hospitalization. We plan to enroll 40 patients.

All eligible subjects will be asked to participate in the study regardless of race, gender, age, or other characteristic except those outlined in the exclusion criteria below. Patients who meet inclusion criteria will be asked to participate in the study by the study team after permission obtained from the treating provider. If they agree, informed consent will be obtained by a study team member.

An additional cohort of providers care for patients on 9cc including nurses, nursing assistants, physicians, advanced practice providers, physical therapists, occupational therapists, students and residents will be asked to participate in the study. If they agree, informed consent will be obtained by a study team member. A maximum of 50 providers were be included in provider cohort.

Given feedback from providers and findings through analysis of RTLS, the study recognizes the need to confirm the validity of RTLS during various ambulatory patterns. This requires enrollment of an additional 22 patients. This additional cohort--**High Intensity Interval Training (HIIT) Cohort**--will be randomly divided into two cohorts: Group 1, Continuous Ambulation (n = 12), and Group 2, Interval Ambulation (n =10).

4.1 Inclusion criteria -- Patient

- 4.1.1 Male or female patients between the ages of 18 and 90.
- 4.1.2 Admitted to 9cc.
- 4.1.3 Recovering from surgery.
- 4.1.4 Ability to understand and the willingness to sign an IRB-approved informed consent document.
- 4.1.5 Ability to understand and complete the study survey instruments in English.

4.2 Exclusion criteria -- Patient

- 4.2.1 Non-surgical patient.
- 4.2.2 Emergency surgical procedure.
- 4.2.3 Anticipated discharge less than 24 hours.
- 4.2.4 Unable to ambulate or ambulation not permitted by treating provider.
- 4.2.5 Unable to understand and complete the study survey instruments in English.

Feasibility Assessment of the Wake Forest Real-time Tracking System for Monitoring Patient Movement during Postoperative Recovery: Part 2
IRB 00039439

4.2.6 Post-operative complications that in the opinion of the study investigator would impair the ability of the patient to adhere to the study procedures.

4.3 Inclusion of women and minorities

Men and women of all races and ethnicities who meet the above-described eligibility criteria are eligible to participate in this study.

5.0 Methods

The proposed study will be completed on 9cc in Wake Forest Baptist Health. Study subjects will be recruited on 9cc in Wake Forest Baptist Health after approval from the treating physician. Recruitment, consent, and data collection will be completed in the privacy of the patient's room.

The nature, purpose, and risks of all procedures and protocols will be explained to each participant prior to obtaining written consent. All examiners are trained in the standardized conduction of all assessments before data collection. Standardized written instructions will be provided.

Subjects will not be recruited for the observational study cohort as this cohort is closed to enrollment.

Enrollment will be limited to the additional the expanded **HIIT Cohort (n= 22)**. Using random number generator, eligible patients will be randomized into two groups: Group 1, Continuous Ambulation (n = 12), and Group 2, Interval Ambulation (n =10). Assignment will be provided by the study coordinator. The study PI will be blinded to this randomization.

Provider participants will be enrolled if they are caring for patients on 9cc during the study period.

5.1a Study timeline (Observational Cohort)

	Initial Visit	Day 1	Day 2	Day 3
Informed Consent	X			
Medical Record Review	X			
Vital Signs	X	X	X	X
Walking Assessment		X	X	X
Fatigue Assessment		X	X	X
Pain Assessment		X	X	X
Walking Distance Measurement		X	X	X
Step/Pedometer Evaluation ¹		X	X	X

Feasibility Assessment of the Wake Forest Real-time Tracking System for Monitoring
Patient Movement during Postoperative Recovery: Part 2
IRB 00039439

Distribution of SPOT Badge	X			
Physical Activity in Hospital Survey				X

¹ Patients will wear a Fitbit Zip™ and Kenz Lifecorder EX Accelerometer for pedometer evaluation.

5.1b Study timeline (HIIT Cohort)

	Initial Visit	Ambulatory Evaluation
Informed Consent	X	
Medical Record Review	X	
Vital Signs	X	X
Walking Assessment		X
Grip Assessment		X
Pedometer Evaluation ¹		X
Distribution of SPOT Badge ²	na	
Patient Survey		X

¹ Patients will wear a Kenz Lifecorder EX Accelerometer for pedometer evaluation during walking assessment.

² SPOT badges are now worn by all inpatients at WFBH and no longer require badging specifically for this project.

